---------------------------------------------------------------------------------------------------------------------------------------------------------------------------------------------------------------------------	--------------------------------------

EPIDEMIOLOGY AND DATA ANALYSIS

[name], CORESEARCH, Pescara
 

 
Signature
	
20-09-2022
 
Date

---------------------------------------------------------------------------------------------------------------------------------------------------------------------	--------------------------------------

INVESTIGATOR PROTOCOL APPROVAL

CLiGaN

“Early start corticosteroids versus standard care (RASBs followed by corticosteroids) for proteinuria in Immunoglobulin A Nephropathy (IgAN) patients with active renal lesions identified by kidney biopsy and RASBs combined with corticosteroids versus sodium-glucose cotransporter2 inhibitor combined with RASBs for proteinuria and renal function in IgAN patients with chronic renal lesions identified by kidney biopsy. **A PROJECT FOR TWO MULTICENTRE, PROSPECTIVE OPEN LABEL RANDOMIZED CLINICAL STUDIES TO EVALUATE THE EFFECT OF TARGETED THERAPY BASED ON KIDNEY BIOPSY FINDINGS IN IgAN PATIENTS (CLiGaN)**”

I agree to the terms of this study protocol. I will conduct the study according to the procedures specified herein, and according to principles of Good Clinical Practices and local regulations and requirements.

Investigator:

Name: _____

Signature: _____

Date: _____

SYNOPSIS

Study Title
	
“Early start corticosteroids versus standard care (RASBs followed by corticosteroids) for proteinuria in Immunoglobulin A Nephropathy (IgAN) patients with active renal lesions identified by kidney biopsy and RASBs combined with corticosteroids versus sodium-glucose cotransporter2 inhibitor combined with RASBs for proteinuria and renal function in IgAN patients with chronic renal lesions identified by kidney biopsy. A PROJECT FOR TWO MULTICENTRE, PROSPECTIVE OPEN LABEL RANDOMIZED CLINICAL STUDIES TO EVALUATE THE EFFECT OF TARGETED THERAPY BASED ON KIDNEY BIOPSY FINDINGS IN IgAN PATIENTS (CLiGaN)”

Protocol Number
	
CLiGaN

Study Phase
	
III

Study Design:
	
The flow of this group of two prospective, multicentre, open-label randomized clinical trials on IgAN patients (CLiGaN) based on the kidney biopsy findings, is illustrated in the figure:


Target Patients
	
Men and women aged 18 to 75 years with biopsy-proven IgAN will be enrolled in the CLiGaN project

Background and study rationale	
Idiopathic Immunoglobulin A nephropathy (IgAN) is the most common glomerulonephritis in the world. It is more prevalent in Asia than in Europe and the US. IgAN is estimated to affect more than 500.000 people in Europe and it is the leading nephritis in kidney-biopsied patients. Approximately 40% of IgAN patients reach end-stage kidney disease (ESKD) 20 years after their kidney biopsy. The high prevalence of ESKD shows that IgAN has a significant economic impact in the countries because renal replacement therapy is costly. Moreover, the disease's onset in the second and third decades of life represents a social challenge because patients are typically very active and highly productive in the workplace. This challenge is one more reason to move from a generalized therapy for all IgAN patients to personalized therapy.
 
The first edition of the KDIGO guidelines, published in 2012 and based on existing evidence from randomized controlled trials, suggested different therapeutic approaches for IgAN patients based on the clinical setting. Three sets of patients were considered:
 
i) Patients with low risk manifest minor urinary findings and proteinuria < 0.5 g/day, normal estimated glomerular filtration rate (eGFR) and normal blood pressure; they need only annual or biannual checks without therapy. They represent only 5-10% of the IgAN patient population.ii) Patients with intermediate risk have proteinuria >0.5 g/day with normal or reduced eGFR and normal or high blood pressure. They may benefit from continuous supportive therapy (renin-angiotensin system blockers; RASBs) when proteinuria lowers less than 1g/day, and eGFR remains stable. When proteinuria is > 1g/day and eGFR (normal at baseline) declines to >50 ml/min/1.73 m², after three months of continuous supportive therapy, patients may benefit from corticosteroids combined with supportive therapy for six months. When eGFR is less than 30 ml/min or between 30 and 50 ml/min/1.73 m², only supportive treatment is recommended with no immunosuppression, except for patients with rapidly progressive glomerulonephritis.iii) Patients at high risk for acute or rapid loss of eGFR caused by rapidly progressive glomerulonephritis or nephrotic syndrome may benefit from corticosteroids combined with immunosuppressive agents and supportive therapy. These patients represent 2-5% of the IgAN population. In the presence of acute kidney injury (AKI) caused by red blood cells stacked in the tubules during the macrohematuria episode, only supportive therapy is suggested. These indications have been confirmed in the recent edition of the KDIGO 2021 guidelines (5). 
Unfortunately, due to the lack of experimental evidence from randomized controlled trials in this setting, the KDIGO guidelines could not consider the presence of active and chronic renal lesions at the time of the kidney biopsy as a potential effect modifier that could drive treatment decisions; this knowledge, nonetheless, is well recognized in clinical practice where patients with chronic renal lesions do not seem to respond to immunosuppressive treatment as opposed

---------------------------------------	-----------------------------------------------------------------------------------------------------------------------------------------------------------------------------------------------------------------------------------------------------------------------------------------------------------------------------------------------------------------------------------------------------------------------------------------------------------------------------------------------------------------------------------------------------------------------------------------------------------------------------------------------------------------------------------------------------------------------------------------------------------------------------------------------------------------------------------------------------------------------------------------------------------------------------------------------------------------------------------------------------------------------------------------------------------------------------------------------------------------------------------------------------------------------------------------------------------------------------------------------------------------------------------------------------------------------------------------------------------------------------------------------------------------------------------------------------------------------------------------------------------------------------------------------------------------------------------------------------------------------------------------------------------------------------------------------------------------------------------------------------------------------------------------------------------------------------------------------------------------------------------------------------------------------------------------------------------------------------------------------------------------------------------------------------------------------------------------------------------------------------------------------------------------------------------------------------------------------------------------------------------------------------------------------------------------------------------------------------------------------------------------------------------------------------------------------------------------------------------------------------------------------------------------------------------------------------------------------------------------------------------------------------------------------------------------------------------------------------------------------------------------------------------------------------------------------------------------------------------------------------------------------------------------------------------------------------------------------------------------------------------------------------------------------------------------------------------------------------------------------------------------------------------------------------------------------------------------------------------------------------------------------------------------------------------------------------------------------------------------------------------------

	
to those with active renal lesions. Observational studies support these clinical findings and their number, consistency and effect sizes shown for interventions based on the findings of kidney biopsy provide equipoise for the design and conduct of randomized trials based on the specific hypothesis that response may be modified by the baseline kidney biopsy findings. Our clinical study in IgAN patients (CLiGaN) will consider, first, the type of renal lesions, and will enrol patients in the ACiGaN and CHRONiGaN study based on current recommended practice (RASB followed by steroids) versus a differential approach (early start steroids or SGLT2) based on the biopsy findings.

Study objectives
	
Primary objectives:
 
 • To evaluate the therapeutic effect on proteinuria with early corticosteroid therapy, administered after the kidney biopsy in IgAN patients with active renal lesions (ACiGaN) versus standard care of RASBs alone followed by corticosteroids combined with RASBs; • To evaluate the therapeutic effect of SGLT2i (Dapagliflozin) combined with RASBs versus corticosteroids combined with RASBs on proteinuria in patients with chronic or moderate renal lesions (CHRONiGaN); thus, to avoid the potential side effects of corticosteroid therapy. 
Secondary objectives:
 
 • To evaluate the effect of study treatments on the renal function and on the progression of the kidney damage in IgAN patients at 3 years • after the prediction of ESKD through our IgAN CDSS tool (DialCheck) at the time of the kidney biopsy, to determine whether this personalized approach to therapy delays the impairment of the renal function.

Endpoints
	
Primary endpoint:
 
 • Between-arms difference in proteinuria reduction within 4 months and in non-responders within 8 months in ACiGaN study. • Between-arms difference in proteinuria reduction within 10 months in CHRONiGaN study. 
Secondary endpoints:
 
 • eGFR slope calculated as mean of individual slope obtained from individual linear regression of eGFR overtime (3 years); • eGFR decline > 40 % from the baseline value; • composite end point: GFR decline > 40%, ESKD (defined as long-term GFR ≤ 15 ml/min/1.73m² for more than three months or need for maintenance dialysis or kidney transplantation) or death due to kidney disease; • absolute difference between last GFR value and baseline GFR; • stable renal function defined as a decline in GFR ≤ 5 ml/min/1.73m² at the end of three years follow- up; • mean annual change in the slope of the reciprocal of serum creatinine concentration;

	
 time-averaged proteinuria (TA-P) calculated as the weighted mean of all post-randomisation measurement, with weights representing the time elapsed since the previous measurement; proteinuria slope, calculated as a mean of individual slope, obtained from individual linear regression of daily proteinuria overtime (3 years); complete remission of proteinuria defined as achievement of urinary protein level ≤ 0.2 g/day or a urinary protein-to-creatinine ratio ≤ 0.2 g/g; partial remission of proteinuria defined as achievement of a urinary protein reduction $\geq 50\%$ or greater compared with the baseline value.
Number of Sites	Over 30
Number of patients	
432 patients:
 
 132 patients (66 patients per group, including a 10% dropout rate, in the ACiGaN trial) 300 patients (150 patients per group, including a 10% dropout rate, in the CHRONiGaN trial)
Inclusion and exclusion criteria	
Inclusion Criteria:
 
ACiGaN study
 
 Males and females aged 18 to 75 years Written informed consent form. Biopsy-proven idiopathic IgAN with active renal lesions (E1 and/or C1) within 2 weeks. eGFR ≥ 30 ml/min/1.73 m². 24 hour proteinuria ≥ 0.5 g. Patients on treatment or candidate for the treatment with RASBs (either an ACEi or ARB), as per clinical practice, according to the current KDIGO guidelines. 
CHRONiGaN study
 
 Males and females aged 18 to 75 years Written informed consent form. Biopsy-proven idiopathic IgAN with chronic (T1,2) or moderate (M0,1, S0,1, E0, T0, C0) renal lesions at high or very high CKD risk within 4 weeks. eGFR ≥ 30 ml/min/1.73 m². 24 hour proteinuria ≥ 0.5 g. Patients on treatment or candidate for the treatment with RASBs (either an ACEi or ARB), as per clinical practice, according to the current KDIGO guidelines. 
Exclusion Criteria:
 
 Non biopsy-proven IgAN

	
 2. IgAN patients with minimal change disease at kidney biopsy and nephrotic syndrome. 3. IgAN patients with macrohematuria and acute renal failure. 4. IgAN patients with rapidly progressive glomerulonephritis (extracapillary lesions in more than 25 % of glomeruli in the kidney biopsy). 5. Patients with secondary IgAN (lupus nephritis, Schoenlein-Henoch purpura, liver cirrhosis). 6. Patients with superimposed IgAN in a kidney transplant. 7. Patients with other types of glomerular diseases. 8. Patients with solitary kidney. 9. Patients with end-stage kidney disease. 10. Bleeding disorders not responsive to treatment. 11. Patients with myocardial infarction or cerebrovascular stroke in the previous six months. 12. Severe liver diseases, infections, malignancies. 13. Uncontrolled diabetes (glycemia > 200 mg/dL and HbA1c > 7.5%). 14. Aseptic necrosis of any bone. 15. Any prior immunosuppressive therapy. 16. Other morbidities that can be exacerbated by corticosteroids. 17. Previous adverse side effects and/or contraindications to RASBs and SGLT2is. 18. Pregnancy and breastfeeding. 19. If women of childbearing potential (WOCBP): patients not available to use highly effective contraceptive measures during the study treatment period and up to one month after the last dose of study drugs.

Study Products
	
Methylprednisolone succinate and prednisone (Corticosteroids, CS) Dapagliflozin (Sodium-glucose cotransporter 2 inhibitor, SGLT2i)

Treatments
	
ACiGaN Study
 
IgAN Active renal lesions
 
Experimental arm: Corticosteroids + RASBs (4 months) → RASBs (4 months) → RASBs (28 months)
 
Control arm (KDIGO): RASBs (4 months) → RASBs + Corticosteroids (4 months) → RASBs (28 months)
 <hr/> 
CHRONiGaN Study
 
IgAN Chronic renal lesions Moderate renal lesions
 
Experimental arm: RASBs (4 months) → RASBs + Dapagliflozin (6 months) → RASBs + Dapa (26 months)
 
Control arm (KDIGO): Run-in → RASBs + Corticosteroids (6 months) → RASBs (26 months)
 
Patients will be randomized separately in each trial (allocation 1 to 1 ratio). Stratified randomization will be done by age and sex in renal centers.
 
ACiGaN trial
 
Experimental arm: Early corticosteroids therapy combined with RASBs followed by RASBs treatment.
 
Control arm (standard care): RASBs treatment followed by corticosteroids combined with RASBs and then only RASBs.
 
CHRONiGaN trial
 
Experimental arm: RASBs therapy followed by Dapagliflozin combined with RASBs.
 
Control arm (standard care): RASBs therapy followed by Corticosteroids combined with RASBs and then RASBs alone

Sample Size and Statistics
	
ACiGaN. Data from the literature have shown a difference in renal survival between corticosteroids and controls when the researchers assumed a difference of 50% in the primary end point (i.e., in the between-arms difference of delta 24 hour proteinuria from base-line to 6 months) as clinically relevant. Therefore, we assume that a mean delta proteinuria from base-line to 6 months in patients treated with RASBs alone (control arm) is 0.6 ± 1.0 g/24 hours (\pmSD) versus a mean delta proteinuria 1.2 ± 1.0 g/24 hours (\pmSD) from base-line to 6 months in patients treated with RASBs and corticosteroids (experimental arm). Based on these assumptions, we calculated a sample size of 132 patients (66 patients per group including a 10% dropout rate) for a power of 90%, a two-sided significance level of 0.05 and 3 years

	
of recruitment. If the number of the enrolled patients will not reach the expected sample size within the established timeframe, the recruitment period will be extended for two additional years.
 
CHRONlGaN. Data from the literature have shown a difference of renal survival between SGLT2is and controls. There are no data in the literature exploring the difference of renal survival or proteinuria between SGLT2is and steroids. Here, the researchers assumed an opportunistic sample of 300 patients for this first comparative study (150 patients per group, including a 10% dropout rate).

Planned study timelines	
Enrollment period: 3 years
 
Treatment and Follow-up period: 3 years + 30 days

LIST OF ABBREVIATION

ACEi	Angiotensin Converting Enzyme inhibitors
ACiGaN	IgAN patients with ACtive renal lesions
AE	Adverse Event
AKI	Acute Kidney Injury
ARB	Angiotensin Receptor Blockers
AZA	Azathioprin
BrdU	Bromodeoxyuridine
C	Extracapillary proliferation, crescents
CDSS	Clinical Decision Support System
CHRONiGaN	IgAN patients with CHRONic renal lesions
CI	Confidence Interval
CKD	Chronic Kidney Disease
CKD-EPI	Chronic Kidney Disease Epidemiology Collaboration
COVID-19	COronaVirus Disease 2019
CRO	Contract Research Organization
CS	Corticosteroids
CSR	Clinical Study Report
CXCL6	C-X-C Motif Chemokine Ligand 6
CYP	Cyclophosphamide
DEFA4	Defensin Alpha 4
DEGs	Differentially Expressed Genes
E	Endocapillary hypercellularity
ECG	Electrocardiogram
eCRF	electronic Case Report Form
eGFR	Estimated Glomerular Filtration Rate
ELISA	Enzyme-Linked Immunosorbent Assay
ESKD	End-Stage Kidney Disease
FACS	Fluorescence-activated Cell Sorting
FAR2	Fatty Acyl-CoA Reductase 2
g/24 hours	gram per 24 hours
g/day	gram per day
g/g	grams per grams
GCP	Guideline for Good Clinical Practice
Gd-IgA1	Galactose-deficient Immunoglobulin A1
GEE	generalized estimating equations
GFR	Glomerular Filtration Rate
HbA1c	Hemoglobin A1c
ICH	International Conference on Harmonization
IgA	Immunoglobulin A
IgAN	Immunoglobulin A nephropathy
IgG	Immunoglobulin G
IHC	ImmunoHistoChemistry,

IP	Investigational Product
ITGAX	Integrin Subunit Alpha X
KDIGO	Kidney Disease: Improving Global Outcomes
LMM	Linear Mixed Models
LTB	Lymphotoxin Beta
M	Mesangial hypercellularity
m ²	square metre
MD	Medical Doctor
mEq/L	milliequivalents per Litre
MESTC-score	mesangial (M) and endocapillary (E) hypercellularity, segmental sclerosis (S), interstitial fibrosis/tubular atrophy (T), crescents (C) score
mg/day	milligram per day
mg/dL	milligram per deciliter
mg/kg	milligram per kilogram
mg/kg/bw	milligram per kilogram of body weight
min.	Minute
ml/min	milliliter /minute
MMF	Mycophenolate Mofetil
mmHg	millimeter of mercury.
PBMC	Peripheral Blood Mononuclear Cell
PI3K/Akt	Phosphatidylinositol 3-kinase/protein kinase B
RASBs	Renin-Angiotensin System Blockers
RCTs	Randomized Controlled Trials
RNA	RiboNucleic Acid
RT-PCR	Reverse Transcription -Polymerase Chain Reaction
S	Segmental glomerular sclerosis
SAE	Serious Adverse Event
SD	Standard Deviation
SGLT2i	Sodium-Glucose co-Transporter-2 Inhibitor
T	Tubular atrophy/interstitial fibrosis
TA-P	Time-Averaged Proteinuria
TNFAIP6	Tumor Necrosis Factor Alpha Induced Protein 6
TNFR	Tumor Necrosis Factor Receptor
WNT-B-catenin	Wnt/β-catenin pathway
WOCBP	Women of ChildBearing Potential

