1.2. Rationale

In our CLlIgAN study, we have planned to evaluate:

- (i) The effect of early start corticosteroid therapy combined with RASBs (experimental arm) versus RASBs alone in IgAN patients with active renal lesions (AClIgAN) who will receive corticosteroids after 4 months of RASBs (standard care) in presence of persistent proteinuria ≥ 0.5 g/24 hours and eGFR ≥ 30 ml/min/1.73 m² (control arm).
- (ii) The effect of SGLT2i (dapagliflozin) combined with RASBs (experimental arm) versus corticosteroids combined with RASBs (control arm) in IgAN patients with chronic or moderate renal lesions (CHRONlIgAN) after a run-in phase of 4 months in which they will receive RASB therapy alone (standard care).

In both studies patients enrolled in the control arms will be treated according to the evidence-based recommendations (standard care) provided within the KDIGO guidelines.

In conclusion, we would like to evaluate the effect of early start corticosteroids in IgAN patients with active renal lesions (AClIgAN) and to spare corticosteroids therapy in IgAN with chronic or moderate renal lesions (CHRONlIgAN) administering Dapagliflozin.

We would also provide earlier ESKD risk prediction by using our tool DialCheck (32).

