4.4 Outcome measures

The primary endpoint is the 24 h-proteinuria reduction between arms as suggested by Inker LA et al (44). It will be assessed after 4 and 8 months in the ACiGaN study and after 10 months in the CHRONiGaN trial.

The secondary end point is the GFR slope calculated as the mean of individual slope obtained from individual linear regression of eGFR overtime (3 years). Based on the International Consensus definition of clinical trial outcomes for kidney failure (23) we have also considered other secondary end points listed below.

Primary and secondary end points that will be evaluated in the two RCTs are listed below:

Primary endpoint:

- Between-arms difference in proteinuria reduction within 4 and 8 months in ACiGaN and within 10 months in CHRONiGaN study.

Secondary endpoints:

- eGFR slope calculated as mean of individual slope obtained from individual linear regression of eGFR overtime (3 years);
- eGFR decline > 40 % from the baseline value;
- composite end point: GFR decline > 40%, ESKD (defined as long-term GFR \leq 15 ml/min/1.73m² for more than three months or need for maintenance dialysis or kidney transplantation) or death due to kidney disease;
- absolute difference between last GFR value and baseline GFR;
- stable renal function defined as a decline in GFR \leq 5 ml/min/1.73m² at the end of three years follow-up;
- mean annual change in the slope of the reciprocal of serum creatinine concentration;
- time-averaged proteinuria (TA-P) calculated as the weighted mean of all post-randomization measurement, with weights representing the time elapsed since the previous measurement;
- proteinuria slope, calculated as a mean of individual slope, obtained from individual linear regression of daily proteinuria overtime (3 years);
- complete remission of proteinuria defined as achievement of urinary protein level \leq 0.2 g/day or a urinary protein-to-creatinine ratio \leq 0.2 g/g;
- partial remission of proteinuria defined as achievement of a urinary protein reduction \geq 50% or greater compared with baseline value.

The end points will be evaluated monthly in IgAN patients with active renal lesions in the first eight months after kidney biopsy and then every three months. In IgAN patients with chronic or moderate renal lesions the end points will be evaluated every three months in the first two years after the enrollment and then every six months.

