6. SAMPLE SIZE AND STATISTICAL METHODS

ACIGAN. Data from the literature (22,23) have shown a difference in renal survival between corticosteroids and controls when the researchers assumed a difference of 50% in the primary end point (i.e. in the between-arms difference of delta 24 hour proteinuria from baseline to 6 months) as clinically relevant. Therefore, we assume that a mean delta proteinuria from baseline to 6 months in patients treated with RASBs alone (control arm) is 0.6 ± 1.0 g/24 hours (\pm SD) versus a mean delta proteinuria that is 1.2 ± 1.0 g/24 hours (\pm SD) from baseline to 6 months in patients treated with RASBs and corticosteroids (experimental arm). Based on these assumptions, we calculated a sample size of

132 patients (66 patients per group including a 10% dropout rate) for a power of 90%, a two-sided significance level of 0.05 and 3 years of recruitment. If the number of the enrolled patients will be insufficient, the recruitment period will be extended for two years.

CHRONiGaN. Data from the literature (29-31) have shown a difference of renal survival between SGLT2is and controls. There are no data in the literature exploring the difference of renal survival or proteinuria between SGLT2is and steroids. Here, the researchers assumed an opportunistic sample of 300 patients for this first comparative study (150 patients per group, including a 10% dropout rate).

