6.4 Statistical Methods

Quantitative variables will be summarized in the presence of normal distribution values as mean \pm SD or median, and interquartile ranges in the presence of non-normally distributed variables. The between-arms comparisons of continuous variables will be performed by independent t-test or Mann-Whitney U test, as appropriate. The between-arms difference of the primary end point (i.e. in the between-arms difference of delta 24h proteinuria from baseline to 6 months in the ACiGAN trial and the between-arms difference of delta 24h proteinuria from baseline to 12 months in the CHRONiGAN trial will be expressed as mean difference and 95% CI. Categorical variables will be presented as absolute and percentage frequency. Proportions will be compared using the Pearson's X^2 test or Fisher's test, as appropriate. The time to event analysis will be performed by the Kaplan-Meier curves by comparing the experimental and control group by the log rank test. Multivariate analysis will be based on Cox's regression proportional hazard method and used to assess the relative risk associated with possible baseline prognostic factors such as sex, age, serum creatinine, eGFR, hypertension, histological lesions and therapy.

The primary analysis will be conducted according to the intention-to-treat approach in all randomized patients, irrespective of adherence to the assigned treatment. A per protocol analysis will be also performed. A secondary analysis by linear mixed models (LMM) or generalized estimating equations (GEE) of repeated measurements of eGFR and proteinuria will be also performed. The choice between the two analyses will closely depend on the distribution type of the outcome variables in our study cohorts.

In these models, data will be expressed as regression coefficients, 95% CIs and P value. All analyses will be performed using SPSS for Windows, 17.0 (SPSS Inc., North Sydney, Australia) and STATA/IC 13.1 for Windows (College Station, Texas, US). A *P* value less than 0.05 will be considered statistically significant.

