6.5 Analysis populations

The primary trial efficacy analysis will be done in the intention-to-treat (ITT) population, including all randomly assigned participants.

A secondary analysis will be performed in the persistent population (PP, i.e. including all patients who persisted on the investigational drugs for at least 4 and 8 months (ACiGaN trial) or 10 months (CHRONiGaN trial).

Patients who need to change their study treatment prior to 1st month (ACiGaN trial) or 4 months (CHRONiGaN trial) will be considered as dropouts.

The safety population will be represented by all patients receiving at least one dose of the investigational drugs.

A recent systematic review (15) evidenced that patients with histological lesion M1 were responsive to corticosteroids. Therefore, we will do a subgroup analysis to evaluate the effect of corticosteroids in active and chronic IgAN patients with lesion M1 versus M0.

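### The synopsis restricts the 8-month part of the ACiGaN primary endpoint to non-responders, a subset shaped by treatment; the body of the protocol contradicts it on population and on time point.

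*Protocol*

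**What the plan says.** - **Synopsis, Endpoints.** The ACiGaN primary endpoint is "Between-arms difference in proteinuria reduction within 4 months and in non-responders within 8 months in ACiGaN study". The protocol does not define a non-responder for this endpoint.
- **Section 4.4.** The same endpoint appears without the restriction: "Between-arms difference in proteinuria reduction within 4 and 8 months in ACiGaN and within 10 months in CHRONiGaN study". On timing: "It will be assessed after 4 and 8 months in the ACiGaN study and after 10 months in the CHRONiGaN trial".
- **Section 6.4.** The primary comparison is the between-arm difference in "delta 24h proteinuria from baseline to 6 months in the ACiGAN trial", analysed by intention to treat. The only significance rule is general: a P "value less than 0.05 will be considered statistically significant".
- **Section 6.5.** "The primary trial efficacy analysis will be done in the intention-to-treat (ITT) population, including all randomly assigned participants".
- **Section 6 and the synopsis sample size.** 66 patients per arm, based on one difference in change from baseline to 6 months, "for a power of 90%, a two-sided significance level of 0.05 and 3 years of recruitment".
- **Section 1.2.** The nearest text to a response rule concerns control patients, "who will receive corticosteroids after 4 months of RASBs (standard care) in presence of persistent proteinuria" of at least 0.5 g/24 hours (with an eGFR condition). It describes who goes on to corticosteroids and does not define an analysis set.

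**The concern.** By month 4 the experimental arm has received corticosteroids plus RASBs and the control arm RASBs alone (Section 3). Whether a patient has responded by then is an outcome of the assigned treatment. Selecting on it leaves experimental patients who did not respond to corticosteroids, who then continue on RASBs alone. They are compared with control patients who have not yet had corticosteroids and are about to receive them. Randomisation does not protect that comparison, and it does not answer the primary objective in Section 2.1, which is early against delayed corticosteroids in the patients randomised.

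There is a second problem. Months 4 and 8 are both named as primary, month 6 is what the trial is sized and analysed on, and nothing says how a result at one time point relates to a result at another. Two analysts following the same protocol could report different primary results.

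**Working it through.** **1. The plan's own sample size.** Inputs from Section 6: difference 1.2 − 0.6 = 0.6 g/24 h, SD 1.0, two-sided 0.05, power 90%, dropout 10%.

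n per arm = 2 × (1.960 + 1.282)² × 1.0² / 0.6² = 58.4, so 59 evaluable. 59 / 0.9 = 65.6, so 66 per arm and 132 in total. The stated figure reproduces exactly. It covers one comparison in all patients.

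**2. What selecting non-responders does.** From the protocol: mean reductions 1.2 and 0.6, SD 1.0, 59 evaluable per arm. My assumptions: these means apply at month 4; the true mean month-8 reduction is equal in both arms (1.2, SD 1.0); a non-responder has a month-4 reduction below a cut c of 0.5 or 1.0 g/24 h; the correlation ρ between a patient's month-4 and month-8 reductions is 0.3 to 0.7; values are normal.

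The share of non-responders in an arm is Φ(c − m), with m the arm's month-4 mean. Their expected month-8 reduction is 1.2 − ρ·λ(c − m), where λ(z) = φ(z)/Φ(z). The spurious difference, experimental minus control, is −ρ × [λ(c − 1.2) − λ(c − 0.6)].

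- c = 0.5: shares 24% and 46%; λ = 1.290 and 0.863; the bracket is 0.428.
- c = 1.0: shares 42% and 66%; λ = 0.929 and 0.562; the bracket is 0.368.

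Rejection rates are from a simulated two-sided t-test at 0.05 within the subset (20,000 trials of 59 per arm):

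| Cut c | ρ | Spurious difference (g/24 h) | Rejects | Of which favouring experimental |
|---|---|---|---|---|
| 0.5 | 0.3 | −0.13 | 6.7% | 1.0% |
| 0.5 | 0.5 | −0.21 | 10.6% | 0.4% |
| 0.5 | 0.7 | −0.30 | 18.8% | 0.1% |
| 1.0 | 0.3 | −0.11 | 7.2% | 0.8% |
| 1.0 | 0.5 | −0.18 | 12.2% | 0.4% |
| 1.0 | 0.7 | −0.26 | 20.8% | 0.1% |

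A normal approximation to the same test gives 7% to 23%. The subset is also small. Even for an unbiased 0.6 g difference, power is 54% if 40% of each arm are non-responders (23.6 per arm) and 71% if 60% are (35.4 per arm).

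**3. Two primary time points.** This applies only if success at either month 4 or month 8 counts and each is tested at two-sided 0.05. The error is one minus the bivariate normal probability that neither test rejects:

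| Correlation of the two tests | Either test rejects (two-sided) | Experimental falsely declared superior |
|---|---|---|
| 0.3 | 9.5% | 4.8% |
| 0.5 | 9.1% | 4.5% |
| 0.7 | 8.4% | 4.2% |

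The nominal values are 5% and 2.5%.

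**4. Time points side by side.** Synopsis endpoint: 4 months, and 8 months in non-responders. Section 4.4: 4 and 8 months. Synopsis sample size, Section 6 and Section 6.4: 6 months. The sample size describes controls as on RASBs alone, yet under Section 3 the control arm starts corticosteroids after month 4. The month to which the 0.6 and 1.2 g figures belong is therefore itself unclear.

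**The case against.** The restriction appears only in the synopsis. The endpoint, analysis and population sections in the body carry none, no test within non-responders is described, and the phrase may loosely echo the treatment pathway in Section 1.2. On that view this is a synopsis–body inconsistency with an undefined term, not a settled plan. That is fair as to origin, but the synopsis still words it as the primary endpoint, and one of two incompatible populations has to be withdrawn.

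Three stronger readings are tempting and not supported:

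- **That months 4 and 8 are each tested at 0.05.** No sentence says so. It can only be inferred from the general P-value rule, and Section 6.4 names a single comparison at 6 months. If success were required at both time points, type I error would hold and power would fall. The figures in step 3 are conditional. For falsely claiming experimental benefit the relevant range is 4.2% to 4.8%, not 8.4% to 9.5%.
- **That false rejection reaches 30% to 48%.** A lognormal model with non-response taken as less than a 50% reduction gives such figures. But its baseline and treatment factors are not in the protocol, and a 50% reduction is used there only for the secondary partial-remission endpoint. Under the same model, persistent proteinuria of at least 0.5 g gives 5% to 8%, with bias of either sign.
- **That the flaw manufactures success.** In the step 2 scenarios nearly all false rejections favour control. The harm is lost power and a misleading result against early treatment.

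**Conclusion.** The point stands in this form. A primary comparison in month-4 non-responders is not a randomised comparison and cannot meet the intention-to-treat requirement. Under the step 2 assumptions it is biased by 0.11 to 0.30 g/24 h against the experimental arm, up to half of the 0.6 g the trial is designed to detect, and it rejects in about 7% to 21% of trials when there is no month-8 difference. The cut and the correlation are assumed because the protocol gives neither, so these figures indicate scale only; that the subset is not comparable between arms does not depend on them.

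Separately, the protocol gives three different months for one primary comparison and no rule linking months 4 and 8. That is a contradiction on the page. Inflated type I error would follow only if success at either month counted.

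**What to change.** - Delete the restriction to non-responders from the synopsis and analyse every primary time point in all randomised patients.
- Name one primary time point, or a fixed order for months 4 and 8 in which the second is tested at 0.05 only if the first succeeds. Which month leads is the sponsor's choice. At month 4 the controls have had no corticosteroids, so state that any claim about early against delayed corticosteroids rests on the month-8 comparison in all randomised patients.
- Align the synopsis (endpoints and sample size) and Sections 4.4, 6 and 6.4 with that choice, including the month to which the 0.6 and 1.2 g assumptions apply.
- Report non-responders by arm descriptively, under a stated definition, with no between-arm test.

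**Cost.** With one time point or a fixed order, alpha stays at 0.05 and N at 132, provided the assumed difference can be re-justified at the chosen month. Splitting alpha instead (0.025 each) would need 69 evaluable and 77 randomised per arm, 154 in total; at 59 evaluable, power per time point would fall from 90.3% to 84.6%. What is given up is a formal test in non-responders, which would not have been a valid comparison of the randomised strategies.
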